2.4 Past or present MS symptoms with Location

Number of each MS symptom/location/persistency/severity by prior and post fingolimod treatment will be provided for the Safety Set.

All past and present MS symptoms will be listed for the Safety Set.

2.5 MS previous therapies

All MS previous therapies will be coded by medication name and will be summarized by preferred term.

2.6 Fingolimod treatment / compliance / Dose interruption

The duration of fingolimod treatment exposure (days) for patients who took at least one dose of fingolimod treatment will be summarized with descriptive statistics. Duration will be calculated as:

Duration of exposure (days) = (Date of last administration of fingolimod treatment – Date of first administration of fingolimod treatment) +1 .

The actual number of days of fingolimod treatment exposure will be calculated as:

Actual days of fingolimod treatment exposure = (Date of last administration of fingolimod treatment – Date of first administration of fingolimod treatment) +1 – days not on treatment.

Compliance(%) will be calculated as:

Compliance (%) = actual days of fingolimod treatment exposure / duration of exposure *100

2.7 Analysis of the primary objective

2.7.1 Primary endpoint

All analyses will be conducted by cohort for the Safety Set. There are 22 primary endpoints for this study, and Change from Baseline to Month 6 will be calculated as:

Change from baseline to Month 6 = Observed Value at Month 6 (Days 136 to 270) – Baseline Value

1. Change from Baseline to Month 6 in CD4+ naïve T cells (CCR7+CD45RA+)
2. Change from Baseline to Month 6 in CD4+ central memory T cells (CCR7+CD45RACD45RO+)
3. Change from Baseline to Month 6 in CD4+ effector memory T cells (CCR7-CD45RACD45RO+)
4. Change from Baseline to Month 6 in CD4+ Th1 cells (CXCR3+)
5. Change from Baseline to Month 6 in CD4+ Th2 cells (CCR4+)
6. Change from Baseline to Month 6 in CD4+ Th17 cells (CCR6+)
7. Change from Baseline to Month 6 in CD8+ naïve T cells (CCR7+CD45RA+)
8. Change from Baseline to Month 6 in CD8+ central memory T cells (CCR7+CD45RACD45RO+)
9. Change from Baseline to Month 6 in CD8+ effector memory T cells (CCR7-CD45RACD45RO+)
10. Change from Baseline to Month 6 in naïve B Lymphocytes (CD19+CD27-)
11. Change from Baseline to Month 6 in memory B Lymphocytes (CD19+CD27+)
12. Change from Baseline to Month 6 in regulatory B Lymphocytes (CD19+CD24+CD38+)
13. Change from Baseline to Month 6 in monocytes (CD14+)
14. Change from Baseline to Month 6 in neutrophils (CD16+)
15. Change from Baseline to Month 6 in NK cells (CD56+)
16. Change from Baseline to Month 6 in Total CD4+ Absolute Cell Counts
17. Change from Baseline to Month 6 in Total CD4+ Differential Cell Counts
18. Change from Baseline to Month 6 in Total CD8+ Absolute Cell Counts
19. Change from Baseline to Month 6 in Total CD8+ Differential Cell Counts
20. Change from Baseline to Month 6 in Total CD19+ Absolute Cell Counts
21. Change from Baseline to Month 6 in Total CD19+ Differential Cell Counts

Descriptive statistics (sample size, mean, standard deviation, standard error of mean, minimum, first quartile, median, third quartile, interquartile range, and maximum) will be provided. The 95% confidence interval for the mean will be calculated.

Analyses will be performed with respect to the actual value of primary variables by employing an analysis of covariance (ANCOVA) model with gender as a factor and duration of disease at Baseline (either time since first symptom or time since diagnosis) and corresponding baseline as covariates. The unadjusted as well as the adjusted least squares means will be provided together with a p-value.

Percent change from baseline mean will also be reported.

2.7.2 Statistical hypothesis, model, and method of analysis

The majority of analyses will be descriptive in nature. The 95% confidence intervals will be provided for the parameters of interest.

This is an open-label, single arm study, and has no active control. And there is no confirmatory hypothesis to be tested. Thus, the multiplicity adjustment of the level of significance for the primary analysis is not relevant in this study.

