9.4 Analysis of the primary variable(s)

9.4.1 Primary Variable(s)

All analyses will be conducted by cohort for the Safety Set.

The primary variables are:

1. Change from Baseline to Month 6 in CD4+ naïve T cells (CCR7+CD45RA+)
2. Change from Baseline to Month 6 in CD4+ central memory T cells (CCR7+CD45RA-CD45RO+)
3. Change from Baseline to Month 6 in CD4+ effector memory T cells (CCR7-CD45RA-CD45RO+)
4. Change from Baseline to Month 6 in CD4+ Th1 cells (CXCR3+)
5. Change from Baseline to Month 6 in CD4+ Th2 cells (CCR4+)
6. Change from Baseline to Month 6 in CD4+ Th17 cells (CCR6+)
7. Change from Baseline to Month 6 in CD8+ naïve T cells (CCR7+CD45RA+)
8. Change from Baseline to Month 6 in CD8+ central memory T cells (CCR7+CD45RA-CD45RO+)
9. Change from Baseline to Month 6 in CD8+ effector memory T cells (CCR7-CD45RA-CD45RO+)
10. Change from Baseline to Month 6 in naïve B Lymphocytes (CD19+CD27-)

11. Change from Baseline to Month 6 in memory B Lymphocytes (CD19+CD27+)
12. Change from Baseline to Month 6 in regulatory B Lymphocytes (CD19+CD24+CD38+)
13. Change from Baseline to Month 6 in monocytes (CD14+)
14. Change from Baseline to Month 6 in neutrophils (CD16+)
15. Change from Baseline to Month 6 in NK cells (CD56+)

Descriptive statistics (sample size, mean, standard deviation, standard error of mean, minimum, first quartile, median, third quartile, interquartile range, and maximum) will be provided. The 95% confidence interval for the mean will be calculated.

Analyses will be performed with respect to the actual value of primary variables by employing an analysis of covariance (ANCOVA) model with gender as a factor and duration of disease and corresponding baseline as covariates. The unadjusted as well as the adjusted least squares means will be provided together with a p-value.

Percent change from baseline mean will also be reported.

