9.7 Interim analyses

As previously mentioned, two interim analyses of data will be performed prior to the final analysis at Month 12.

1. The first interim analysis is an early assessment to evaluate safety of Cohort 2 patients. This will be conducted when 50% of patients in Cohort 2 have completed the Month 6 follow up. For this analysis, primary variables, demographics, baseline characteristics, adverse events, and serious adverse events will be summarized.
2. The second interim analysis is the primary analysis for this study. This analysis will be conducted when all patients in Cohorts 1 and 2 complete Month 6 (primary time point of interest) of study. All data collected on patients from both Cohorts 1 and 2 will be included in this analysis. These data will be analyzed as mentioned in Sections [9.4](#), [9.5](#), and [9.6](#).

This is an open-label, single arm study, and has no active control. The first interim analysis is a summarization of data from Cohort 2 only and no confirmatory hypothesis will be tested. Thus, the multiplicity adjustment of the level of significance for the primary analysis due to the first interim analysis is not relevant in this study. Results obtained from these interim analyses may be reported and published externally for communication to health care professions, as appropriate.

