9.8 Sample size calculation

Cohort 1: A sample size of 200 patients will be able to detect an effect size of 0.30 with 89% power after adjusting for multiplicity of testing changes in 15 primary variables, at an overall significance level of 0.05.

In addition, for both cohorts the primary interest is to estimate mean change from Baseline at various time points (Months 3, 6, and 12) of the primary and secondary variables. A sample

size of 200 patients in each cohort will provide us the precision of estimates within 0.14 of the corresponding standard deviation of the variables of interest.

10 Ethical considerations

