2.1 Data analysis general information

Interim analysis/final analysis will be performed [REDACTED]

SAS® Software version 9.4 or later will be used in this study as primary statistical analysis software.

Statistical methods used in reporting for both efficacy and safety are described below.

In general, categorical measurements will be summarized by frequency counts and percentages. Continuous variables will be summarized by numbers of patients, means, standard deviations, standard error of mean, first quartile, medians, third quartile, interquartile range, minimums, and maximums.

In summary statistics of means and medians, one more decimal place beyond the reported data will be displayed, and 2 more decimal places will be displayed for the standard deviation. The minimum and maximum will keep the same decimal places as the reported data.

Statistical tests will be performed at a 2-sided significance level of 0.05 unless otherwise stated. All p-values will be rounded up to 4 decimal places. For example, any p-value strictly greater than 0.0049 and less than or equal to 0.0050 will be displayed as 0.0050. This guarantees that on any printed statistical output, the unrounded p-value will always be less than or equal to the displayed p-value. A displayed p-value of 0.0001 will always be understood to mean ≤ 0.0001 . Likewise, any p-value displayed as 1.0000 will be understood to mean > 0.9999 and ≤ 1 .

All collected data from the eCRFs (including electronic data) and derived analytical data will be included in the listing.

All summaries will be presented by Cohort.

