2.9 Interim analysis

Two interim analyses of data will be performed prior to the final analysis at Month 12.

1. The first interim analysis is an early assessment to evaluate safety in Cohort 2 patients. This will be conducted when 50% of patients in Cohort 2 have completed the Month 6 follow up. For this analysis, primary variables, demographics, baseline characteristics, adverse events, and serious adverse events will be summarized.
2. The second interim analysis is the primary analysis for this study. This analysis will be conducted when all patients in Cohorts 1 and 2 complete Month 6 (primary time point of interest) of study. All data collected on patients from both Cohorts 1 and 2 will be included in this analysis. These data will be analyzed as mentioned in protocol Sections 9.4, 9.5, and 9.6.

This is an open-label, single arm study, and has no active control. The first interim analysis is a summarization of data from Cohort 2 only and no confirmatory hypothesis will be tested. Thus, the multiplicity adjustment of the level of significance for the primary analysis due to the first interim analysis is not relevant in this study. Results obtained from these interim analyses may be reported and published externally for communication to health care professions, as appropriate.

3 Sample size calculation

Cohort 1: A sample size of 200 patients will be able to detect an effect size of 0.30 with 89% power after adjusting for multiplicity of testing changes in 15 primary variables, at an overall significance level of 0.05.

In addition, for both cohorts the primary interest is to estimate mean change from Baseline at various time points (Months 3, 6, and 12) of the primary and secondary variables. A sample size of 200 patients in each cohort will provide us the precision of estimates within 0.14 of the corresponding standard deviation of the variables of interest.

4 Change to protocol specified analyses

Not applicable.

5 Appendix

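### The 89% power claim assumes a multiplicity adjustment over 15 variables, but the SAP applies no adjustment and lists 21 primary endpoints while declaring 22

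*SAP*

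**What the plan says.** **Power statement.** SAP 3 says that 200 Cohort 1 patients will "detect an effect size of 0.30 with 89% power after adjusting for multiplicity of testing changes in 15 primary variables". Protocol 9.8 has the same sentence, which ends "after adjusting for multiplicity of testing changes in 15 primary variables, at an overall significance level of 0.05".

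**Analysis.** SAP 2.7.2 states that no confirmatory hypothesis is tested and concludes: "Thus, the multiplicity adjustment of the level of significance for the primary analysis is not relevant in this study". The general rule in SAP 2.1 is "Statistical tests will be performed at a 2-sided significance level of 0.05 unless otherwise stated", and no section sets a stricter level for the primary endpoints. SAP 2.7.1 and 5.2.1 still call for an ANCOVA p-value for each primary endpoint.

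**Scope of the waiver.** The protocol's only multiplicity statement is in 9.7 and is narrower: "the multiplicity adjustment of the level of significance for the primary analysis due to the first interim analysis is not relevant in this study". SAP 2.9 repeats that narrow form. SAP 2.7.2 drops the reference to the interim look and waives adjustment for the primary analysis as a whole.

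**Number of endpoints.** Protocol 9.4.1 lists 15 primary variables. SAP 2.7.1 says "There are 22 primary endpoints for this study", but its numbering runs unbroken from 1 to 21 and ends with "21. Change from Baseline to Month 6 in Total CD19+ Differential Cell Counts". Items 16 to 21 (total CD4+, CD8+ and CD19+ cells, each as absolute and differential counts) are not in protocol 9.4.1. SAP 4, the place to record changes from the protocol's analyses, declares none.

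**The concern.** The sample-size section and the analysis section of one SAP describe different studies. One adjusts 15 tests to hold an overall 0.05; the other runs 21 tests per cohort at 0.05 each with nothing held overall. A reader of the report could meet a justification that invokes an overall 0.05 level beside 21 unadjusted Cohort 1 p-values and take those p-values to be controlled. The first interim and the primary analysis may both be published externally (protocol 9.7, SAP 2.9), so this is not only an internal matter.

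Six primary endpoints were also added without being recorded as a change. The report would then carry primary endpoints that the protocol does not name and that the power statement does not cover.

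**Working it through.** **Inputs.** From protocol 9.8, SAP 3 and SAP 2.1: n = 200, effect size d = 0.30, overall level 0.05, k = 15 variables, two-sided tests. From SAP 2.7.1: k = 21 listed. *Assumptions:* the documents name neither the adjustment nor the null hypothesis of the ANCOVA p-value, so I use Bonferroni (0.05/k) and a one-sample t-test of mean change.

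**Step 1: reproduce the plan's figure.** Noncentrality = d√n = 0.30 × √200 = 4.243, with 199 degrees of freedom. At 0.05/15 = 0.00333 the two-sided critical value is 2.971, and the noncentral t gives power 89.6%. This matches the stated 89%, so the arithmetic is sound for 15 adjusted tests.

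**Step 2: the same calculation for what the SAP plans.**

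| Level per test | Critical t | Power at d = 0.30 | Effect detectable with 89% power |
|---|---|---|---|
| 0.05/15 = 0.00333 (power statement) | 2.971 | 89.6% | 0.298 SD |
| 0.05/21 = 0.00238 (SAP list, if adjusted) | 3.078 | 87.6% | 0.305 SD |
| 0.05 (SAP 2.7.2 as written) | 1.972 | 98.8% | 0.226 SD |

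With 22 endpoints, adjusted power would be 87.3%.

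**Step 3: chance of at least one false positive at unadjusted 0.05.** The number m of true nulls among the 21 and their correlation ρ are assumptions. For independent tests the chance is 1 − 0.95^m. For a common correlation ρ it is 1 − ∫ [Φ((1.96 − √ρ·u)/√(1−ρ)) − Φ((−1.96 − √ρ·u)/√(1−ρ))]^m φ(u) du.

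| True nulls m | Independent | ρ = 0.5 | ρ = 0.7 | Expected false positives (0.05m) |
|---|---|---|---|---|
| 5 | 22.6% | 18.3% | 14.8% | 0.25 |
| 10 | 40.1% | 28.7% | 21.3% | 0.50 |
| 21 | 65.9% | 42.9% | 29.5% | 1.05 |

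The last row is an upper bound. It is not realistic for Cohort 1, because protocol 1.1 and 3.2 expect large falls in several subsets. Some true nulls are plausible, since protocol 1.1 describes effector memory T cells as mostly spared.

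**Step 4: the precision basis.** The half-width of the 95% interval in SD units is t(0.975, n−1)/√n = 1.972/14.142 = 0.139 at n = 200, which agrees with the stated 0.14. It does not depend on multiplicity. It does need 200 evaluable Month 6 pairs: discontinued patients are not replaced (protocol 4) and nothing is imputed (SAP 2.7.3). At an assumed loss of 10%, 15% or 20% (180, 170 or 160 pairs) the half-width is 0.147, 0.151 or 0.156 SD. Power at 0.05/15 is then 85.1%, 82.3% or about 79%.

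**The case against.** The best defence is that the study is descriptive and says so. The overall 0.05 appears only in a planning sentence, and SAP 2.7.2 disclaims confirmatory testing. Planning at a strict level and then reporting descriptively is conservative: power is 98.8% unadjusted and only 1.4 points below the stated 89% at 21 adjusted tests. The precision target, which both documents call the primary interest, is met. The 15 in the power statement matches protocol 9.4.1, so the protocol lacks an adjustment procedure but does not contradict itself. The 22 is probably a miscount, because SAP 2.8.2 carries the same 21 cell variables to Months 3 and 12. The false-positive rates rest on assumed nulls and correlations, and absolute and differential counts of one cell population are unlikely to be independent.

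Much of this stands. The sample size is adequate on the plan's own terms, the false-positive rates are illustrative, and the 22 is editorial. It does not remove the conflict. If the study is descriptive, the adjusted-power sentence should not be in the SAP; if that sentence is meant, SAP 2.7.2 is wrong. Primary p-values are still to be produced, and even 5 true nulls with correlation 0.7 put the false-positive chance at about three times 0.05. The undeclared addition of six primary endpoints is untouched by the defence.

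**Conclusion.** The concern holds and should be fixed. The 89% is correct for 15 Bonferroni-adjusted two-sided tests in 200 patients, but the SAP plans 21 unadjusted tests and calls them 22. As written, the power figure and the overall 0.05 level are properties that the planned primary analysis does not have.

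The effect on power is small: 87.6% if all 21 endpoints were adjusted, 98.8% if none. The effect on error control is larger: a false-positive chance of 15% to 40% for an assumed 5 to 10 true nulls and correlations from 0 to 0.7, against a stated 5%. Mean changes and their confidence intervals are unaffected, and 200 patients are not shown to be too few. The power figures rest on Bonferroni, a one-sample t-test and 200 evaluable pairs; the documents specify none of these three.

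**What to change.** Make SAP 2.7.2 and SAP 3 agree in one of two ways.

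- **(a) Keep error control.** Name the procedure for the Cohort 1 primary variables. With Bonferroni, test at 0.05/15 if the six added counts become secondary, or at 0.05/21 with power restated as about 87.6% if they stay primary. Holm is also suitable; the Bonferroni power is then a lower bound. Label Cohort 2 p-values nominal.
- **(b) Keep the descriptive position.** Label all p-values nominal, delete the adjusted-power sentence, and rest the sample size on the 0.14 SD precision. This is closer to what SAP 2.7.2 already says.

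In either case:

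- correct 22 to the true count;
- record the six added endpoints and the multiplicity position in SAP 4;
- state the null hypothesis that the ANCOVA p-value tests;
- state that the precision figure, and the power figure if it is kept, assume 200 evaluable Month 6 pairs.

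The cost is SAP wording only, with no new data or patients. Under (a) fewer subsets will be called significant, and the quoted power falls slightly if all 21 endpoints stay primary. Under (b) the claim of controlled error is given up.

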2.7.3 Handling of missing values/censoring/discontinuations

No imputation will be performed for efficacy endpoints.

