3.6 Risks and benefits

The study involves a FDA approved dose (0.5mg/day) and indication (RMS) of fingolimod. Therefore the study population will be examined within a known benefit/risk profile of fingolimod. Any procedural risks will be minimized using compliance with the eligibility criteria as well as optimal study procedures.

Patients will receive the benefit of being systematically monitored over a 12 Month period at regular follow-ups for immune phenotype profiling, which would not have taken place during normal routine follow up Visits.

4 Population

The study population will consist of male and female patients (≥ 18 years of age) with a diagnosis of MS. In the first cohort approximately 200 patients with RMS, who are newly prescribed commercially available fingolimod 0.5mg/day will participate in the study. In the second cohort approximately 200 RMS patients who have been on commercially available fingolimod 0.5mg/day continuously for at least ≥ 2 years will participate in the study.

The goal is to include 400 patients (Cohort 1, n=200 and Cohort 2 n=200) from up to 125 centers in the United States. Since a 25% screen failure rate is expected, approximately 533 patients will be screened.

Patients who discontinue after they have been enrolled will not be replaced.

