5.1 Imputation rules

In general, other than for partial dates, missing data will not be imputed and will be treated as missing.

Partial date will be imputed as below:

- If year is missing (or completely missing), do not impute;
- 15th of the month will be used to impute the initial diagnosis date if only the day is missing;
- July of the year will be used to impute as the initial diagnosis date if both the day and the month are missing;

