5.2 Statistical models

5.2.1 Primary analysis

The primary statistical analysis will use an analysis of covariance (ANCOVA) model with gender as a factor and the duration of disease and baseline as covariates. The primary analysis population will be the Safety Set. The unadjusted as well as the adjusted least squares means will be provided together with a p-value.

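### The Month 6 primary ANCOVA uses only patients with a Month 6 sample; a repeated-measures model using their Month 3 values would add a little precision and reduce bias if dropout depends on Month 3

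*SAP*

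**What the plan says.** SAP 2.7.1 defines the primary endpoints as the value observed at Month 6 (Days 136 to 270) minus baseline, analysed by cohort in the Safety Set. SAP 5.2.1 names the model: "The primary statistical analysis will use an analysis of covariance (ANCOVA) model with gender as a factor", with disease duration and baseline as covariates. It has no Month 3 term and no repeated-measures structure.

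On missing values, SAP 2.7.3 says "No imputation will be performed for efficacy endpoints". SAP 5.1 is broader: "In general, other than for partial dates, missing data will not be imputed and will be treated as missing". Protocol 9.4.3 likewise rules out imputation for both safety and efficacy data, and Protocol 9.4.4 marks sensitivity analyses as not applicable. Protocol section 4 adds: "Patients who discontinue after they have been enrolled will not be replaced".

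Month 3 blood samples are taken (Protocol Table 6-1). Their changes from baseline are summarised as separate secondary variables (SAP 2.8.2) and enter the correlation analyses (SAP 5.2.2).

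SAP section 3 gives the planned size. For Cohort 1, "A sample size of 200 patients will be able to detect an effect size of 0.30 with 89% power". That power figure allows for 15 primary variables being tested, with 0.05 as the overall level. For both cohorts, "A sample size of 200 patients in each cohort will provide us the precision of estimates within 0.14 of the corresponding standard deviation".

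**The concern.** With one visit in the model and nothing imputed, a patient with baseline and Month 3 samples but no Month 6 sample contributes nothing to the primary estimate, although that patient belongs to the Safety Set named as the analysis population. This has two consequences.

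- **Precision.** The stated power and precision use the full enrolled number, with no allowance for missing Month 6 samples and no replacement of dropouts.
- **Bias.** The ANCOVA adjusts for baseline but not for how the patient had responded by Month 3. If patients with unusually low or high Month 3 values are more likely to be missing at Month 6, the observed-case mean is shifted. The documents make this possible without establishing it: the outcomes are immune-cell measures, Protocol Appendix 2 lists low lymphocyte counts as notable, and Protocol 5.5.6 lets patients leave on the basis of safety assessments. No planned analysis would show whether it had happened.

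**Working it through.** **Inputs from the documents.** n = 200 per cohort, effect size 0.30, 89% power, 15 variables and overall significance level 0.05 (SAP section 3). Tests are two-sided: "Statistical tests will be performed at a 2-sided significance level of 0.05 unless otherwise stated" (SAP 2.1). Planned precision is 0.14 SD (SAP section 3).

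**Inputs assumed, because the documents do not give them.**
- Share missing at Month 6: d = 10% to 20%.
- Every patient missing Month 6 has a Month 3 sample.
- Correlation of Month 3 with Month 6 *given baseline*: r = 0.4 to 0.7.
- For bias, patients missing Month 6 differ by 0.5 SD at Month 3 from those observed.
- SD is treated as equal at the two visits.

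**Step 1: reproduce the plan.** The precision is 1.96/√200 = 0.139 SD, stated as 0.14. For power, a one-sample two-sided t test at 0.05/15 = 0.00333 with n = 200 and effect size 0.30 gives 89.6%, close to the stated 89%. Both figures need all 200 patients to have a Month 6 value. Keeping 0.140 SD takes 196 patients, and keeping 89% power takes 197.

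**Step 2: observed cases only.** The same formulas with n = 200 × (1 − d):

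| d | n | 95% half-width (SD) | Power |
|---|---|---|---|
| 10% | 180 | 0.146 | 85.1% |
| 15% | 170 | 0.150 | 82.3% |
| 20% | 160 | 0.155 | 79.1% |

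**Step 3: which correlation applies.** The ANCOVA already conditions on baseline, so Month 3 adds only what baseline does not explain. If the ordinary correlation were 0.7 between every pair of visits, the correlation given baseline would be (0.7 − 0.7²)/(1 − 0.7²) = 0.21/0.51 = 0.41. Hence the range 0.4 to 0.7.

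**Step 4: precision recovered with Month 3.** In units of SD², variance = (1 − r²)/n_obs + r²/200, and effective n = 1/variance. At 15% missing:
- r = 0.4: 0.84/170 + 0.16/200 = 0.005741, so effective n = 174.2 and the half-width is 0.148 SD.
- r = 0.7: 0.51/170 + 0.49/200 = 0.005450, so effective n = 183.5 and the half-width is 0.145 SD.

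| d | Observed cases: n, half-width | With Month 3: effective n | With Month 3: half-width (SD) |
|---|---|---|---|
| 10% | 180, 0.146 | 183 to 189 | 0.145 to 0.143 |
| 15% | 170, 0.150 | 174 to 184 | 0.148 to 0.145 |
| 20% | 160, 0.155 | 165 to 177 | 0.152 to 0.147 |

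If only half of those missing Month 6 had a Month 3 sample, effective n at 15% missing and r = 0.7 would be 177 rather than 184.

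**Step 5: bias of the observed-case mean.** Bias = d × r × 0.5 SD.
- 15% missing: 0.15 × 0.4 × 0.5 = 0.03 SD to 0.15 × 0.7 × 0.5 = 0.05 SD.
- 20% missing: 0.20 × 0.4 × 0.5 = 0.04 SD to 0.20 × 0.7 × 0.5 = 0.07 SD.

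Against the planned 0.14 SD, this is roughly a fifth to a half of the half-width.

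**Step 6: check by simulation.** Dropout odds were made to rise 1.5- to 2-fold per SD of the Month 3 value, with r = 0.5 to 0.7. The observed-case bias was 0.03 to 0.07 SD at 15% missing and 0.04 to 0.09 SD at 20%. Coverage of the nominal 95% interval at 15% missing fell to between 93% and 86%. Using Month 3 brought the bias to about zero, as expected when dropout depends only on the observed Month 3 value.

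**The case against.** The case for leaving the plan alone has several sound parts.

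- **The study is descriptive.** SAP 2.7.2 says that no confirmatory hypothesis is tested, and the sample size will be shown with each summary, so losses will be visible. This limits the weight of the power figures. It does not answer the bias, because SAP section 3 gives estimation of mean change as the primary interest.
- **Some dropouts still count.** Protocol 5.6.2.1 asks for a discontinuation visit, Table 6-1 includes blood sampling there, and any sample in Days 136 to 270 is assigned to Month 6 (SAP 2.1.1). This reduces the loss. Patients who leave earlier have their last sample in the Month 3 window, where the primary model does not use it.
- **The inputs are not in the documents.** This stands. The only rate given, 25%, is screen failure before enrolment and says nothing about missing Month 6 samples. No text links subset counts to stopping, and Cohort 2 patients have already been on treatment for at least two years.
- **The no-imputation rule is deliberate.** It can stay: a likelihood-based repeated-measures model imputes nothing.

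A reader might also infer that the plan throws away the Month 3 data. It does not: they are reported as secondary results and are unused only in the Month 6 estimate. Nor do the documents support saying that a mixed model would remove dropout bias altogether. That holds only under missing at random.

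**Conclusion.** The point holds as an inexpensive improvement to the primary analysis. The Month 6 estimate is an observed-case analysis with no planned check on missing values, and data already collected could inform it.

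Under the assumptions listed, the precision gain is modest: at 15% missing, the half-width goes from 0.150 SD to about 0.148 to 0.145 SD. The main reason to change is protection against dropout that depends on the Month 3 value. If dropouts differ by 0.5 SD at Month 3, that bias is about 0.03 to 0.05 SD at 15% missing and 0.04 to 0.07 SD at 20%. A lower correlation given baseline, fewer Month 3 samples among dropouts, or fewer missing Month 6 samples would shrink both benefits.

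A reader might go further and conclude that the primary result is biased or the study underpowered. The documents support neither, since the amount and cause of missing data are unknown.

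**What to change.** For each cohort and primary variable, estimate the Month 6 least squares mean change with its 95% CI from a likelihood-based repeated-measures model on Months 3 and 6. Include visit, baseline, baseline-by-visit, gender and disease duration, with an unstructured covariance.

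- Keep the single-visit ANCOVA as a supportive analysis.
- Report, by cohort, how many Safety Set patients have a Month 6 sample.
- Add Month 12 only at the final analysis. The primary analysis runs when all patients have reached Month 6, so Month 12 will be incomplete then.
- State how discontinuation-visit samples taken off drug are handled, since the visit windows can place them at Month 3 or Month 6.

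The cost is SAP wording and slightly more programming, with no new data. The model relies on missing at random and does not protect against dropout driven by the unobserved Month 6 values.
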